Provide a clear, concise narrative of study procedures with special attention to the subjects' involvement. Detail the overall study timeline and location of study procedures, list all interventions, assessments and interviews, estimate the duration of each procedure, provide dosing schedules, identify study personnel involved in each procedure, and provide credentials for relevant personnel. For complicated study designs, we strongly encourage attaching tables, flow-charts, and study algorithms.

In the R61, we will confirm target engagement of D-serine + auditory remediation, assess relationships of plasticity changes and cognition, safety and assess the optimal dose of D-serine treatment. In the R33, we conduct a randomized, placebo-controlled, parallel group study with the superior dose of D-serine combined with 16 weekly sessions of the same neuroplasticity-based auditory remediation. The structure of this grant requires successful completion of the R61 phase over 2 years prior to initiation of the R33 phase. We will amend the PSF and consent to include a full description of the R33 phase prior to its initiation.

The study will be conducted in groups of 15 subjects in which 12 subjects will receive D-serine for each of the three treatment visits and 3 will receive placebo for each of the three treatment visits. The first group of 15, will receive 80 mg/kg or placebo, and the second group of 15 subjects will receive 100 mg/kg or placebo, followed by a third group receiving 120 mg/kg or placebo. As previous studies noted minimal carry over effect of D-serine effects ([name] 2010), subjects may be permitted to participate in more than one phase with at least a six

month space in between.

If there are tolerability concerns at the 80 or 100 mg/kg doses, we will add a 60 mg/kg arm, ensuring the assessment of multiple doses. After each cohort, we will obtain permission from both the FDA and the IRB via an amendment, prior to the beginning of the next cohort. We require this safety milestone to be reached in order to begin the next cohort.

R61 Design (Table 1):

R61 Design	Table 1 (R61)	Baseline	Treatment Day			Follow-up ¹
			1	2	3	
		Day -30 to -1	Day 1	Day 8±2	Day 15±2	
	Consent	x				
	Medical screening	x				
	D-serine/Placebo		x	x	x	
	MMN		x	x	x	
	Auditory Remediation/EEG		x	x	x	
	Cognitive and behavioral ratings	x				
	Clinical laboratory/pregnancy/vitals	x	x	x	x	x
	SAFTEE/C-SSRS	x	x	x	x	x
	1. If necessary to follow-up any abnormalities.					

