## **Statistical Analysis Plan & Power**

Before any specific statistical techniques are applied, we will examine all variables at all time points for illegitimate values, outliers, and other inconsistencies. Distributions of demographic variables and other clinically important baseline variables will be examined and summarized by means, standard deviations, minima, and maxima for continuous measures and proportions for categorical measures. We will make every effort to obtain all data to reduce or eliminate missing data issues. Intent-to-treat analysis will be implemented for all estimation and testing. Tests will be two-sided and statistical significance determined by  $p < 0.05$ .

**R61 Component.** Summaries of clinical and demographic variables will be provided for each of the three cohorts (C1) D-serine 80mg/kg (n = 12) vs. placebo (n = 3), (C2) D-serine 100mg/kg (n = 12) vs. placebo (n = 3), and (C3) D-serine 120mg/kg (n = 12) vs. placebo (n = 3). As a precaution, any indication of imbalance on important baseline measures between treatment arms (despite randomization) will trigger investigation of whether differences in the primary outcome measures are attributable to these imbalances. For analyses described below, the placebo groups from each of the three cohorts will be combined to yield an effective placebo group of n = 9, unless descriptive analyses suggest systematic differences between the three placebo groups, in which case the groups will remain separate in subsequent analyses.

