Aim 1 Analysis: Aim 1 hypothesizes that D-serine will lead to greater plasticity, MMN, and theta-ITC changes than placebo, with the largest effect being seen at the 120mg/kg dose. Plasticity improvement (defined as change from trials 20 – 30 to trials 70 – 80 at end of session) in the 3rd week of treatment will be examined by using Cohen's d effect size estimates. Within each D-serine group, Cohen's d for within-subject change will be computed by taking the mean change in plasticity divided by the pre-treatment standard deviation. Similar Cohen's d values will be computed for the combined placebo group. Corresponding 95% confidence intervals (based on standard theory or constructed via bootstrapping if assumptions for constructing the confidence intervals based on parametric methods are not satisfied) will be computed. Similar procedures will be followed for assessing within-subject changes in MMN and theta-ITC. For each D-serine dose level, Cohen's d for between-group differences will be computed as (mean change for the D-serine group minus mean change for the placebo group) divided by standard deviation of the change scores in the combined placebo group.

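### The between-group d rests on a nine-patient placebo SD with no stated small-sample correction, and the SAP does not say which SD or placebo mean applies if the placebo groups are kept separate

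*SAP*

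**What the plan says.** - **Denominator.** In the SAP (R61 Component, Aim 1 Analysis), the between-group d for each dose is mean change on D-serine minus mean change on placebo, "divided by standard deviation of the change scores in the combined placebo group". No small-sample factor appears in the SAP text available.
- **Confidence intervals.** The 95% intervals, "based on standard theory or constructed via bootstrapping", are introduced after the within-subject d. The between-group d is defined later, and no interval is stated for it.
- **Placebo group.** The R61 Component has three cohorts of 12 D-serine and 3 placebo patients. The nine placebo patients are combined "unless descriptive analyses suggest systematic differences between the three placebo groups, in which case the groups will remain separate in subsequent analyses". No criterion is given. The same paragraph begins "Summaries of clinical and demographic variables will be provided for each of the three cohorts", so the look may concern baseline variables, but this is not stated.
- **Expected ordering.** Aim 1 expects greater changes than on placebo, "with the largest effect being seen at the 120mg/kg dose".
- **Sequence.** Under Study Procedures in the Protocol, the 80 mg/kg cohort comes first, then 100 mg/kg, "followed by a third group receiving 120 mg/kg or placebo". FDA and IRB permission is required "prior to the beginning of the next cohort". Also, "subjects may be permitted to participate in more than one phase", at least six months apart.

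**The concern.** An SD from nine patients varies widely, and dividing by it pushes d upward on average. The between-group d values are the SAP's placebo-controlled measure of target engagement, so an uncorrected d presents the drug slightly too favourably.

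The second issue is a choice left open until data are in hand. If the look is taken to show systematic differences, the groups are to stay separate, yet the formula names only the combined group. The analyst would then have to decide which placebo mean to subtract and which SD to divide by. The choice also bears on the dose ordering: cohorts run one after another, so dose and cohort order coincide, and a combined placebo mean offers no protection against a shift between cohorts.

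**Working it through.** **Inputs.** From the SAP: 12 patients per dose; placebo 3 × 3 = 9, which reproduces the stated n = 9; total 3 × (12 + 3) = 45, which matches the Protocol. Assumed: normal and independent change scores, all 45 complete, equal spread unless stated. The documents give no number for the moderate effect in the go/no-go rule. I assume 0.5 and show 0.45 and 0.56, because the Protocol background calls 0.45 moderate and 0.56–0.86 moderate-large.

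**1. Bias.** The exact small-sample factor is J(m) = Γ(m/2) / [√(m/2) · Γ((m−1)/2)]. J(8) = 0.903, and 1/0.9027 = 1.108, an inflation of 10.8%. A true 0.50 reads 0.50 × 1.108 = 0.554.

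**2. Error at true d = 0.5.** Let v = 1/12 + 1/9 = 0.1944.
- E(d²) = (8/6) × (0.1944 + 0.25) = 0.5926.
- Variance = 0.5926 − 0.5539² = 0.2858, so the SD is 0.535.
- RMSE as planned = √(0.2858 + 0.0539²) = 0.54.
- Corrected: 0.903 × 0.535 = 0.48, with no bias.

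**3. Chance of reaching the cut-off with no drug effect, one dose and one endpoint.** √v = 0.441. As planned, t = 0.5/0.441 = 1.134 on 8 df. Corrected, t = 0.5/(0.903 × 0.441) = 1.256.

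| Assumed cut-off | As planned | × 0.903 |
|---|---|---|
| 0.45 | 16.9% | 14.6% |
| 0.50 | 14.5% | 12.2% |
| 0.56 | 12.0% | 9.9% |

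**4. What the look can show.** Three means of three patients from one population have an average range of 0.98 SD (simulated 5th–95th percentile 0.25–1.91). Suppose there is a linear drift of D = 0.5 SD from cohort 1 to cohort 3. A 5% F test on 2 and 6 df has noncentrality 6 × (0.25)² = 0.375 and detects the drift in about 7% of trials. At D = 0.94 it does so in 12%. A stated criterion would therefore help little.

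**5. The separate branch.** With an own-cohort placebo mean, the SE of the mean difference rises from 0.441 to √(1/12 + 1/3) = 0.645 SD. Even if the SD were known exactly, P(d ≥ 0.5) with no effect would be P(Z ≥ 0.5/0.645) = 21.9%. The three-patient mean drives this, whatever the denominator.

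**6. Dose ordering.** With combined placebo, the same placebo mean is subtracted at every dose, so it cancels from the 120-minus-80 difference. That difference has SE √(2/12) = 0.41 SD but absorbs any cohort drift in full. As an illustration, with no drug effect and 0.5 SD of drift shared by both arms, 120 mg/kg ranks highest in 69% of simulated trials, against 33% by chance. Within cohorts the drift cancels, but the SE is √(2/12 + 2/3) = 0.91 SD.

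**7. Pooling the SD within arms (41 df, J = 0.982).** With equal spread, RMSE at 0.5 is 0.45 and the null crossing chance is 12.7%. If the D-serine SD is 1.25 times placebo, the pooled SD is √[(8 + 33 × 1.5625)/41] = 1.205 placebo SDs, and a placebo-scale 0.50 reads 0.41. At 0.8 times, the pooled SD is 0.843 and 0.50 reads 0.59.

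**The case against.** **Dividing by the control-group SD is a recognised, prespecified choice.** It keeps the scale free of any drug effect on spread. This stands, and the fix keeps that d.

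**A reader might infer that a corrected pooled SD would cure both problems.** It would not. At SD ratios of 1.25 or 0.8 it shifts a 0.50 by about −17% or +19%, more than the 10.8% removed. It lowers the null crossing chance no further than the one-number correction (12.7% against 12.2%), and it leaves the three-patient mean as imprecise as before. In its favour, it has lower RMSE with equal spread, and also at ratio 1.25 despite the bias.

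**A reader might infer that the separate branch has no computable denominator, or that d there is inflated by 77%.** The documents do not support either. The nine-patient SD can still be computed. The 77% belongs to an SD from a cohort's own three placebo patients (J(2) = 0.564), which the SAP never names. The defect is ambiguity.

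**No document reports drift between cohorts.** True: the drift values are scenarios. They show what the combined d cannot rule out, not what happened.

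**The go/no-go link is uncertain.** This stands too. The Protocol refers to an application section for the milestone detail, and the effect-size change in its study overview could mean the within-subject d.

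**Conclusion.** The point holds in a limited form. The planned between-group d is biased upward by about 10.8% under normality, and one stated multiplier removes this. Separately, the SAP permits a branch without naming the SD or placebo mean to use, and entry to it depends on a look that cannot tell drift from noise at three patients per group.

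The size is modest. After correction the standard error of d at a true 0.5 is still about 0.48, so imprecision from nine placebo patients remains the larger limitation. The result should not be read as showing that the R61 decision rule is invalid: the 0.5 cut-off is assumed and the governing milestone text is not in these documents. The figures also assume 45 completers and independent records. Repeat participation, which the Protocol allows, would weaken the independence assumption. That no correction is given is judged on the SAP text available.

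**What to change.** Amend the SAP wording for Aim 1:

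1. Keep the placebo-SD d and multiply it by the Hedges factor 0.903 (8 df; recompute if fewer than nine placebo patients contribute).
2. State that the 95% confidence interval also covers the between-group d.
3. Make the combined-placebo d primary whatever the descriptive look shows. Report the three within-cohort d values beside it as descriptive only, never standardised by a three-patient SD, and name the SD used. Note their low precision (SE of the 120-minus-80 difference about 0.91 SD), and that the combined d alone cannot separate dose from cohort order.
4. Report a corrected d with the SD pooled within arms (factor 0.982, 41 df) as a sensitivity analysis only, because it measures a different quantity if the drug alters the spread.

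**Cost.** No new data or patients are needed. The reported d becomes slightly less favourable and there is a little more to report. Keeping combined placebo primary accepts exposure to cohort drift in exchange for precision, which is why the within-cohort values belong beside it.
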